4.1 Safety

Safety is measured by the incidence of adverse events (AEs) and serious adverse events (SAEs) from baseline to Day 60.

The hypotheses to be tested are:

$$H_0: \pi_A = \pi_S \text{ versus } H_A: \pi_A \neq \pi_S$$

Where π_A and π_S represent the proportion of patients who experience an AE or SAE for Ampion and Placebo during the first 60 days after randomization. The difference between Ampion and Placebo will be tested via an appropriate chi-square test or Fisher's exact test utilizing PROC FREQ with the EXACT option, if needed.

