3.2 Secondary Endpoints

Secondary endpoints assess the effect of inhaled Ampion treatment compared to placebo on the clinical outcomes for participants with respiratory distress due to COVID-19 as follows:

Objective	Endpoint
Secondary	
Assess the effect of Ampion compared to placebo on safety	
Incidence of adverse events (AEs) and serious adverse events (SAEs) from baseline to Day 60.
Assess the effect of Ampion compared to placebo on clinical health	
Change in NEWS2 score from baseline through Day 5.Change in NEWS2 score from baseline to hospital discharge.
Assess the effect of Ampion compared to placebo on hospital stay	
Hospital length of stay (LOS) from admission to discharge.
Assess the effect of Ampion compared to placebo on oxygen use	
Change in baseline in oxygen use, blood oxygen saturation, and oxygen flow rate from baseline through Day 5.
Assess the effect of Ampion compared to placebo on progression to respiratory failure	
Percentage of participants who progress to respiratory failure (i.e., need for mechanical ventilation, ECMO, non-invasive ventilation) by Day 28.
Assess the effect of Ampion compared to placebo on intensive care	
Percentage of participants who require Intensive Care Unit (ICU) admission by Day 28.ICU-free days through Day 28.ICU LOS from ICU admission to discharge.
Assess the effect of Ampion compared to placebo on all-cause mortality	
Percentage of participants with a successful outcome (life) or unsuccessful outcome (death) by Day 28.

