Assess the effect of Ampion compared to placebo on intensive care	
Percentage of participants who require Intensive Care Unit (ICU) admission by Day 28.ICU-free days through Day 28.ICU LOS from ICU admission to discharge.

Assess the effect of Ampion compared to placebo on all-cause mortality	
 Percentage of participants with a successful outcome (life) or unsuccessful outcome (death) by Day 28.
--	--

The efficacy endpoints will be evaluated to estimate the treatment effect and use descriptive statistics including mean, standard deviation, percentages, minimum/maximum, and 95% confidence intervals. All endpoints will be tabulated and presented by treatment arm, cohort (moderate and severe), and timepoint. Where appropriate, data will be tabulated and presented cumulatively across cohorts and/or timepoints.

All binary outcomes are single incident percentages and thus the differences between the treatment groups will be tested using Fisher's exact test. The length of stay endpoints are also single incident endpoints the differences between the treatment groups will be tested using two sample t-test. All the other change from baseline variables are repeated assessments and will be analyzed utilizing a repeated measures analysis of variance.

Exploratory endpoints assess the effect of inhaled Ampion treatment compared to placebo on the clinical outcomes for participants with respiratory distress due to COVID-19 as follows:

Objective	Endpoint
Exploratory	
Assess the effect of Ampion compared to placebo on cytokine profile	
 Modulation of cytokine levels from baseline to Day 5.

The efficacy endpoints will be evaluated to estimate the treatment effect and use descriptive statistics including mean, standard deviation, percentages, minimum/maximum, and 95% confidence intervals. All endpoints will be tabulated and presented by treatment arm, cohort (moderate and severe), and timepoint. Where appropriate, data will be tabulated and presented cumulatively across cohorts and/or timepoints.

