4.8 Cytokine Profile

The exploratory endpoint, cytokine profile, is measured as the modulation of cytokine levels from baseline to Day 5.

The hypotheses to be tested are:

$H_0: \mu_A = \mu_S$ versus $H_A: \mu_A \neq \mu_S$

Where μ_A and μ_S represent the mean percent change from baseline in the cytokine levels at day 5 for Ampion and Placebo after randomization. The difference between Ampion and Placebo with respect to the percent change from baseline at day 5 will be tested utilizing a two-sample t-test via PROC TTEST. To assess any potential time trends, an exploratory repeated measures analysis of variance will be performed with terms for treatment, time, and the interaction of the two. This will be done utilizing PROC GLM with the REPEATED option. Also, the rates of the various adverse events and serious adverse events will be presented in tables, but otherwise not analyzed statistically.

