5. DEFINITIONS

5.1 Adverse Event:

An adverse event (AE) is defined as any undesired medical occurrence in a patient or clinical investigation patient receiving a pharmaceutical product and which does not necessarily have a causal relationship with this treatment. An AE can therefore be any unfavorable sign and unintended sign (including an abnormal laboratory finding), symptom, or disease temporarily associated with the use of a study drug, whether or not related to the study drug.

AEs will be graded for severity using the following categories. Missing grade will be assigned a grade of 3 (severe) in tabulations.

- **Grade 1 (MILD):** The symptom is barely noticeable to the study patient and does not influence performance or functioning. Concomitant medication is not ordinarily indicated for relief of mild AEs.
- **Grade 2 (MODERATE):** The symptom is of sufficient severity to make the study patient uncomfortable and to influence performance of daily activities. Concomitant medication

may be indicated for relief of moderate AEs.

- **Grade 3 (SEVERE):** The symptom causes severe discomfort, sometimes of such severity that the study patient cannot continue in the study. Daily activities are significantly impaired or prevented by the symptom. Concomitant medication may be indicated for relief of severe AEs.

Relationship to study drug will be coded using the following categories. Missing relatedness will be assigned to related in tabulations.

- **Unrelated:** The adverse event is unlikely to have been caused by study drug.
- **Possibly related:** It is unclear whether the adverse event may have been caused by study drug.
- **Related:** The adverse event is likely to have been caused by study drug.

5.2 Serious Adverse Event:

A serious adverse event (SAE) is defined as an adverse event that

- Results in death
- Is life-threatening (patient is at immediate risk of death from the event as it occurred)
- Requires prolongation of existing hospitalization
- Results in persistent or significant disability/incapacity
- Results in a congenital anomaly/birth defect

5.3 Treatment-Emergent AE:

A treatment-emergent AE (TEAE) is any AE that begins or increases in severity after the initial dose of study drug.

5.4 Age:

Subject's age is defined as its integer value in years at enrollment.

5.5 Baseline:

For any variable, unless otherwise defined, baseline is the last assessment taken prior to the first study drug administration.

5.6 Change from Baseline:

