11.1.3 Safety (Analysis population: Safety)

11.1.3.1	Overall Summary of Treatment-Emergent Adverse (TEAE) Events
11.1.3.2	Incidence of TEAEs by System Organ Class and Preferred Term
11.1.3.3	Incidence of Treatment-Emergent Related AEs by System Organ Class and Preferred Term
11.1.3.4	Incidence of Treatment-Emergent Serious Adverse Events (SAEs) by System Organ Class and Preferred Term
11.1.3.5	Incidence of TEAEs by Preferred Term in Descending Order of Frequency
11.1.3.6	Incidence of Treatment-Emergent Related AEs by Preferred Term in Descending Order of Frequency

11.1.3.7.1	Summary of Hematology
11.1.3.7.2	Summary of BioChemistry
11.1.3.8.1	Summary of Vital Signs and Change from Baseline over Time (bpm)
11.1.3.8.2	Summary of ECG Results
11.1.3.8.3	Summary of Medical History
11.1.3.9.1	Concomitant Medication Use by ATC Level 1
11.1.3.9.2	Concomitant Medications Descending Order of Use
11.1.3.9.3	Medication Started on Study in Descending Order of Use
11.1.3.9.4	Concomitant ARDS therapies Started on Study in Descending Order of Use

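### SAP 4.1 tests one pooled AE-or-SAE proportion, which equals any AE, so the SAE incidence named in the safety endpoint has no between-arm comparison of its own

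*SAP*

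**What the plan says.** SAP 3.2 lists the safety endpoint as "Incidence of adverse events (AEs) and serious adverse events (SAEs) from baseline to Day 60", and SAP 4.1 opens the same way: "Safety is measured by the incidence of adverse events (AEs) and serious adverse events (SAEs) from baseline to Day 60". SAP 4.1 then gives a single two-sided hypothesis pair, π_A = π_S against π_A ≠ π_S, where the two parameters "represent the proportion of patients who experience an AE or SAE for Ampion and Placebo during the first 60 days after randomization". One test follows: "The difference between Ampion and Placebo will be tested via an appropriate chi-square test or Fisher's exact test utilizing PROC FREQ".

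SAP 5.2 fixes how the two event classes relate: "A serious adverse event (SAE) is defined as an adverse event that" meets one of the listed seriousness criteria.

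Three other places bear on the point:

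- The general rule in SAP 4: "All binary outcomes are single incident percentages and thus the differences between the treatment groups will be tested using Fisher's exact test".
- A sentence at the end of SAP 4.8, the cytokine section: "Also, the rates of the various adverse events and serious adverse events will be presented in tables, but otherwise not analyzed statistically".
- The table list in SAP 11.1. An AE summary and analysis table appears under efficacy (11.1.2.1). The SAE table under safety (11.1.3.4) is titled "Incidence of Treatment-Emergent Serious Adverse Events (SAEs) by System Organ Class and Preferred Term".

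SAP 4 also says that the secondary endpoints are tested hierarchically in the order listed. Safety is first in that order and all-cause mortality is last.

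**The concern.** If SAEs are a subset of AEs, a patient with an AE or an SAE is a patient with an AE. The words about SAEs then add nothing to the tested quantity, and half of the named endpoint has no comparison.

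This matters because the any-AE proportion is a blunt measure in this population. Patients with severe or critical COVID-19 followed to Day 60 may well mostly have at least one AE in either arm. An imbalance in serious events, in either direction, then moves the any-AE proportion little or not at all. The plan specifies no SAE risk difference or confidence interval that would show it.

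There is a second consequence. Safety is the first step of the hierarchical sequence, so the definition of this proportion also decides what must be shown before later secondary endpoints are formally tested.

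**Working it through.** **Inputs.** 100 per arm (SAP 2.4); final alpha 0.047, two-sided (SAP 7.1); Fisher's exact or chi-square test (SAP 4 and 4.1). The documents give no expected AE or SAE rates, so all such rates below are assumptions.

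**The plan's own figure.** SAP 2.4 claims at least 80% power for deaths of 8% v 26% with 200 patients. The normal approximation gives 92.9% at alpha 0.05 and 92.6% at 0.047. Exact Fisher power is 91.5% and 90.9%. The statement holds as a lower bound. No power is stated for the safety test.

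**Step 1: what is tested.** By SAP 5.2, {SAE} ⊂ {AE}. Hence {AE or SAE} = {AE}, and π in SAP 4.1 is the any-AE proportion.

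**Step 2: SAEs fall on patients who would have had some AE anyway.** The any-AE rates are then equal, and the planned test rejects only at its type I error, however large the SAE gap. Exact Fisher rejection at 0.047:

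| Any-AE rate, both arms | Rejection |
|---|---|
| 60% | 3.6% |
| 80% | 3.2% |
| 90% | 2.5% |
| 95% | 1.9% |

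Worked example with 100 per arm:

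- Any AE, 90 v 90: Fisher p = 1.0.
- SAE, 10 v 30: Fisher p = 0.00065. The risk difference is 20 points, with SE = √(0.10×0.90/100 + 0.30×0.70/100) = 0.0548 and 95% CI 20 ± 1.96×5.48 = 9.3 to 30.7 points.

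**Step 3: a milder model.** Let SAE rates be 8% v 26%, borrowing the plan's mortality rates only as a convenient pair. Let other AEs occur independently at rate q in both arms. Then

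- any AE = 1 − (1 − SAE)(1 − q), so the difference shrinks to 0.18(1 − q);
- power = Φ[(d − 1.986·s₀)/s₁], with s₀ the pooled and s₁ the unpooled standard error of the difference.

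At q = 20%, any AE is 1 − 0.92×0.80 = 26.4% v 1 − 0.74×0.80 = 40.8%. Here d = 0.144, s₀ = 0.0668 and s₁ = 0.0660, so power = Φ(0.17) = 57%.

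| Other-AE rate q | Any AE | Power, normal approximation | Power, exact Fisher |
|---|---|---|---|
| 20% | 26% v 41% | 57% | – |
| 30% | 36% v 48% | 43% | – |
| 50% | 54% v 63% | 24% | 21% |
| 70% | 72% v 78% | 13% | 10% |
| 90% | 91% v 93% | 6% | 4% |

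At q = 90% the normal figure is about 7% if rejections in the opposite tail are counted.

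**Step 4: a separate SAE comparison.** Exact Fisher power at 0.047 for assumed SAE rates: 10% v 30%, 93.2%; 20% v 40%, 84.0%; 10% v 20%, 42.5%. A direct comparison detects large gaps but not modest ones, which is why an interval is worth more than a p-value here.

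**The case against.** **One hypothesis pair may cover several measures.** SAP 4.4 writes one pair for three oxygen measures, which are plainly not pooled, and SAP 4.2 writes one pair after naming two NEWS2 endpoints. On that pattern, SAP 4.1 could mean each incidence in turn, with the general Fisher rule supplying the test. This reading is possible. But SAP 4.4 refers to various measures, and SAP 4.6 says outright that its hypotheses are tested independently. SAP 4.1 has neither: it defines the proportion of patients with one or the other. The Fisher rule names a test and defines no SAE proportion. If two tests were intended, two proportions still need to be written.

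**A reader might infer that a large difference in serious events goes wholly untested or unseen.** The documents do not support that. SAP 4.5 to 4.7 test respiratory failure, ICU admission and death by Day 28. The 8% v 26% pair in the working is the plan's mortality assumption, and SAP 4.7 compares deaths directly. SAEs are tabulated by arm (11.1.3.4), SAP 9.5.1 provides tables or narratives for deaths and serious events, and the DSMB reviews SAEs (Protocol 3.5). What remains is that the separate tests stop at Day 28, omit other SAEs, and come after safety in the hierarchy.

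**A reader might also infer that SAP 4.8 contradicts SAP 4.1.** It need not. Its sentence concerns the various events and can be read as individual event types. Testing overall incidence while only tabulating individual types is coherent. The sentence is misplaced more than wrong.

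**The size depends on unknown rates.** This stands. If other AEs are uncommon (q = 20%), the any-AE test keeps moderate power.

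**Conclusion.** The point holds in a limited form. As written, SAP 4.1 tests any AE, and the SAE incidence named in the endpoint gets no defined between-arm comparison. The gap covers overall SAE incidence, SAEs other than death, respiratory failure and ICU admission, and serious events from Day 28 to Day 60. It is a gap in analysis, not in reporting or oversight, and it does not invalidate the trial.

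Its size depends on how common AEs are, which the documents do not say. If the excess SAEs fall on patients who would have had an AE anyway, the planned test has no power beyond its type I error. Under independence with SAEs of 8% v 26%, power runs from about 57% when other AEs occur in 20% of patients to about 6–7% when they occur in 90%. The conclusion that the tested proportion equals any AE needs none of these assumptions. It follows from SAP 5.2.

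**What to change.** - **SAP 4.1:** define two proportions per arm, any AE and any SAE to Day 60. Report each with the between-arm risk difference and 95% CI.
- **SAP 4:** state whether either comparison is part of the hierarchical sequence and, if so, which result allows testing to continue. Without this, adding the SAE comparison would leave the first step before the later secondary endpoints undefined.
- **SAP 4.8:** move the sentence on AE and SAE rates to the safety section and limit it to individual event types by system organ class and preferred term. Deleting it would remove a useful statement that individual event types are not tested.

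The cost is SAP wording and one more 2x2 table, with no new data. The downside is one more safety comparison, to be reported without an efficacy claim. The change should be made before unblinding.

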4.2 Clinical Health

Clinical health is measured by the change in NEWS2 from baseline to Day 5, and baseline to hospital discharge.

The hypotheses to be tested are:

$$H_0: \mu_A = \mu_S \text{ versus } H_A: \mu_A \neq \mu_S$$

Where μ_A and μ_S represent the mean change from baseline in the NEWS2 score assessment through day 5 for Ampion and Placebo after randomization. The difference between Ampion and Placebo with respect to the change from baseline at day 5, or discharge if earlier, will be tested utilizing a Wilcoxon rank-sum test via PROC NPAR1WAY. To assess any potential time trends an exploratory repeated measures analysis of variance will be performed with terms for treatment, time and the interaction between the two. This will be done utilizing PROC GLM with the REPEATED option.

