### 9.4.2 Secondary Endpoints

Secondary endpoints assess the effect of inhaled Ampion treatment compared to placebo on the clinical outcomes for participants with respiratory distress due to COVID-19. The secondary endpoints will be tested in a hierarchical manner in the order presented, and thus no adjustment to the alpha level is necessary:

Objective	Endpoint
Secondary	
Assess the effect of Ampion compared to placebo on safety	

Incidence of adverse events (AEs) and serious adverse events (SAEs) from baseline to Day 60.

Assess the effect of Ampion compared to placebo on clinical health	

Change in NEWS2 score from baseline through Day 5.

Change in NEWS2 score from baseline to hospital discharge.

Objective	Endpoint
Assess the effect of Ampion compared to placebo on hospital stay	
 
Hospital length of stay (LOS) from admission to discharge.
 

Assess the effect of Ampion compared to placebo on oxygen use	
 
Change from baseline in oxygen use, blood oxygen saturation, and oxygen flow rate from baseline through Day 5.
 

Assess the effect of Ampion compared to placebo on progression to respiratory failure	
 
Percentage of participants who progress to respiratory failure (i.e., need for mechanical ventilation, ECMO, non-invasive ventilation) by Day 28.
 

Assess the effect of Ampion compared to placebo on intensive care	
 
Percentage of participants who require Intensive Care Unit (ICU) admission by Day 28.
 
ICU-free days through Day 28.
 
ICU LOS from ICU admission to discharge.
 

Assess the effect of Ampion compared to placebo on all-cause mortality	
 
Percentage of participants with a successful outcome (life) or unsuccessful outcome (death) by Day 28.
 

The efficacy endpoints will be evaluated to estimate the treatment effect and use descriptive statistics including mean, standard deviation, percentages, minimum/maximum, and 95% confidence intervals. All endpoints will be tabulated and presented by treatment arm, cohort (moderate and severe), and timepoint. Where appropriate, data will be tabulated and presented cumulatively across cohorts and/or timepoints.

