8.1 Handling of Missing and Incomplete Data

All data collected under this study protocol will be included in the assessment of patient safety. Missing or incomplete AE data will assume greatest relationship to study drug and/or severity.

Incomplete adverse event and concomitant medication dates will be imputed as described in Section 11. If imputed dates are used, then they will be identified as such in the final study report. If an AE start date is missing or partially missing and no additional information is available in order to establish whether the event started before or after the dose of study drug, the event will be considered to have started after dose. Partially missing dates where the month and year is prior to Day 0 will not be classified as post dose.

For the ordinal score effectiveness endpoint analysis of clinical outcomes at Day 5 and Day 28 a sensitivity analysis will be performed for all patients that have been discharged from the hospital, cannot be reached via telephone contact, and their death status is not known. The sensitivity analysis will be performed where missing ordinal scale status at Day 5 and Day 28 will be replaced as having died (Ordinal score 8).

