9.6 Efficacy Analyses

The efficacy of treatment on the clinical course and outcome of COVID-19 will be evaluated by comparing to placebo. Summaries will be performed by severity (severe or critical), individually, and combined.

Unless otherwise specified, continuous variables will be summarized with the number of non-missing observations, mean, standard deviation, median, minimum, maximum and 95% confidence intervals displayed. Data transformation or use of rank-based tests may be used if endpoints depart substantially from a normal distribution. Categorical data will be summarized as counts, percentages and 95% confidence intervals.

Differences between treatments will be presented using mean differences and 95% confidence intervals. Endpoints will be compared between treatment groups (Ampion or control).

Except where otherwise specified, missing data will not be estimated or carried forward in any of the descriptive analyses. No multiple comparison adjustment will be done for the secondary efficacy analyses. If the data clearly violate the distribution assumptions of the model, then transformations may be applied, or rank-based methods used.

The efficacy analyses of the endpoints are detailed in Section 3 and Section 4 above.

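### SAP 4.2 gives no rule for death before the NEWS2 assessment, so both NEWS2 tests default to survivors, which matters mainly for change to discharge; that endpoint also lacks its own hypothesis and test

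*SAP*

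**What the plan says.** SAP 4.2 names two endpoints: "Clinical health is measured by the change in NEWS2 from baseline to Day 5, and baseline to hospital discharge". The second is also a listed secondary endpoint in Protocol 9.4.2: "Change in NEWS2 score from baseline to hospital discharge". Both are steps in the hierarchical order of SAP 4, after adverse events and before hospital stay, oxygen use, respiratory failure, intensive care and mortality.

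The hypothesis in SAP 4.2 covers only one of them. Its parameters "represent the mean change from baseline in the NEWS2 score assessment through day 5 for Ampion and Placebo after randomization". The test is on the "change from baseline at day 5, or discharge if earlier, will be tested utilizing a Wilcoxon rank-sum test via PROC NPAR1WAY". Repeated measures ANOVA (PROC GLM with REPEATED) is there labelled exploratory.

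The general text of SAP 4, repeated in Protocol 9.4.2, says otherwise: "All the other change from baseline variables are repeated assessments and will be analyzed utilizing a repeated measures analysis of variance".

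Protocol 5.2 builds NEWS2 from oxygen requirement, SpO2 and vital signs collected at study visits. No NEWS2 rule mentions death. The one rule that puts a value in place of a missing status concerns the ordinal scale, in a sensitivity analysis of discharged patients who cannot be reached: "missing ordinal scale status at Day 5 and Day 28 will be replaced as having died (Ordinal score 8". SAP 9.6 adds: "Except where otherwise specified, missing data will not be estimated or carried forward in any of the descriptive analyses".

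**The concern.** A patient who dies in hospital has no NEWS2 value at discharge, and one who dies before Day 5 has none at Day 5. The wording in SAP 4.2 covers patients who leave hospital early but not those who die. Without a rule, PROC NPAR1WAY omits missing responses, and PROC GLM with REPEATED omits any patient with a missing time point. The comparison is then between survivors, and survival is itself an outcome of treatment.

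If the drug prevents deaths, the Ampion survivors include patients who would have died on placebo. If those patients leave hospital sicker than the others, they pull the Ampion mean in the wrong direction, and the endpoint can count against a drug that saves lives. This sits ahead of mortality in the testing order.

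The second problem is that change to discharge has its own step in the hierarchy but no hypothesis of its own. The only test that reaches it is the general ANOVA sentence. That sentence disagrees with SAP 4.2 on which method is confirmatory, and it fits poorly with a single change measured at a patient-specific time. An unclear test here leaves the later steps unclear too.

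**Working it through.** **The plan's own figure.** The documents give no power for NEWS2. The only power statement is for Day 28 mortality: 8% versus 26%, 100 per arm, at least 80% (SAP 2.4). Two-sided at 0.05 with a pooled normal approximation: mean rate 0.17; null SE = √(2 × 0.17 × 0.83 / 100) = 0.0531; alternative SE = √((0.08 × 0.92 + 0.26 × 0.74) / 100) = 0.0516; z = (0.18 − 1.96 × 0.0531) / 0.0516 = 1.47; power 92.9% (92.6% at 0.047). The statement holds as a lower bound. It says nothing about NEWS2, but it supplies the mortality rates used below.

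**Patients without a score.**
- Discharge, assuming all Day 28 deaths precede discharge: 100 × 0.08 = 8 Ampion and 100 × 0.26 = 26 control, so 34 of 200 (17%), leaving 92 versus 74.
- Day 5: the documents give no Day 5 mortality. If 10%, 25% or 50% of Day 28 deaths occur by then (assumed), the loss is 0.8 versus 2.6, 2 versus 6.5, or 4 versus 13 patients.

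**Simulation.** From the documents: 100 per arm, the mortality rates, and the final two-sided alpha of 0.047. Assumed: NEWS2 change in survivors has mean −4 and SD 2.5, and the share of Ampion patients equal to the mortality difference is "rescued" and ends 2 or 3 points worse. 3,000 trials per scenario, unstratified Wilcoxon. Positive shifts are against Ampion.

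Hand check at 8% versus 26%: rescued share of Ampion survivors = 18/92 = 19.6%, so the expected shift is 0.196 × 2 = 0.39 or 0.196 × 3 = 0.59 points.

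| Day 28 mortality, Ampion vs control | Basis | Survivors-only test significantly favours placebo (2 to 3 points worse) |
|---|---|---|
| 8% vs 26% | plan's assumption | about 15-25% |
| 8% vs 21% | control rate in the Phase I study | about 10-14% |
| 4% vs 13% | assumed, half the plan's rates | about 6-10% |
| Day 5: 0.8% vs 2.6% to 2% vs 6.5% | 10-25% of deaths by Day 5, assumed | about 3-5% |

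With no shift, chance alone gives about 2-3% in that direction. Repeat runs move these figures by one or two points. At 8% versus 26% with SD 4 instead of 2.5, the share is about 8-13%. If half the deaths fell by Day 5, the rates would be 4% versus 13% and the third row would apply.

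**Worst rank for deaths, same model, 8% versus 26%.** With no shift in survivors it rejects in about 60% of trials (35% at 8% versus 21%). With rescued patients 2 or 3 points worse it rejects in about 32% and 22%, essentially always in favour of Ampion. The same data can therefore point in opposite directions under the two rules.

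**A different model.** SD 3, no drug effect on NEWS2, and correlation of 0 to 0.6 between frailty and NEWS2 change. For discharge, the survivors-only difference moves against Ampion by about 0 to 0.5 points, with two-sided rejection of 4.6% to 19.2%; worst rank rejects in 28% to 58%. For Day 5, with 10-50% of deaths by then, the shift is about 0 to 0.3 points and rejection is 4.4% to 8.7%.

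**The case against.** Several stronger readings are tempting, and the documents do not support them.

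- A reader might infer that the plan excludes deaths. It does not say so. The sentence in SAP 9.6 is limited to descriptive analyses, and SAP 6.1.2 puts all randomized patients in every efficacy analysis. The inferential handling is unspecified; survivors-only is what the named procedures do by default. That default stands as the concern, because an ITT definition says who belongs in the analysis, not what value a dead patient takes.
- A reader might infer that change to discharge has no test at all. The general sentence in SAP 4 and Protocol 9.4.2 covers it. What stands is that no test is specific to it and that the general sentence contradicts SAP 4.2.
- A reader might take 5% versus 60% rejection as proof of lost power. With no NEWS2 difference in survivors, about 5% is the correct error rate for a survivors' question; the 60% is the mortality difference showing through.
- A reader might infer that preventing death earns no credit in this trial. Death scores 8 on the primary ordinal scale, and mortality is a separate secondary endpoint. The gap is confined to NEWS2.

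The best remaining objection concerns size. The 2 to 3 point penalty has no source in the documents, Protocol 3.2.1 says progression to ventilation or death has been lower than earlier in the pandemic, and Protocol 4.5 excludes patients whose death is imminent. All three weaken the Day 5 case in particular, and the results are given as ranges for that reason.

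**Conclusion.** The concern holds in this form: SAP 4.2 has no rule for death in either NEWS2 change, and the default is a survivors-only comparison. It is material mainly for change to discharge, where 17% of patients would lack a score at the plan's own rates with unequal loss between arms. The risk of a significant result in the wrong direction there runs from about 6% to 25%, depending on mortality and on an assumed 2 to 3 point penalty in rescued patients, with SD 2.5. At Day 5 it is small under the shares of early deaths considered most closely. Separately, and without any assumption, the discharge endpoint lacks a specific hypothesis and test, and SAP 4 and SAP 4.2 disagree on whether Wilcoxon or repeated measures ANOVA is the test for NEWS2. This should be corrected before unblinding; it does not touch the primary endpoint.

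**What to change.** In SAP 4.2:

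1. State that a patient who dies before the assessment receives the worst rank in the planned Wilcoxon rank-sum test, for both the Day 5 and the discharge endpoint.
2. Write the hypothesis for change to discharge and name that Wilcoxon test for it.
3. Reconcile the general repeated measures sentence in SAP 4 and Protocol 9.4.2 with SAP 4.2, so that one method is confirmatory and the other exploratory.

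The worst-rank rule does not settle patients alive and still in hospital at Day 60; one further line should say how they are handled.

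The cost is wording, with no new data. The downside is that the endpoint becomes a NEWS2/death composite that partly overlaps the ordinal scale and mortality endpoints. Survivor-only NEWS2 summaries should therefore stay as descriptive output; SAP 11.1 and 11.2 list no NEWS2 table or listing at present, so these have to be added.
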